4.7.4. Recording AE, SAE and ADRs

All AEs, including local and systemic reactions not meeting the criteria for AE/SAEs/ADRs, will be captured on the appropriate Adverse Event Form. Information to be collected includes event description, time of onset, clinician's assessment of severity, relationship to study product (assessed only by those with the training and authority to make a diagnosis), and time of resolution/stabilization of the event.

All AEs occurring while on study must be documented appropriately regardless of relationship. All AEs will be followed to adequate resolution.

Any medical condition that is present at the time that the participant is screened will be considered as baseline and not reported as an AE. However, if the study participant's condition deteriorates at any time during the study, it will be recorded as an AE.

Changes in the severity of an AE will be documented to allow an assessment of the duration of the event at each level of severity to be performed. AEs characterized as intermittent require documentation of onset and duration of each episode.

4.7.5. Reporting of Fatal or Life Threatening or Serious Unexpected ADRs

- **Fatal or Life-Threatening Unexpected ADRs**

All SAEs should be reported to local DSMB within 24 hours of known information by the PI/investigators.

Certain ADRs may be sufficiently alarming so as to require very rapid notification to regulators in countries where the medicinal product or indication, formulation, or population for the medicinal product are still not approved for marketing, because such reports may lead to consideration of suspension of, or other limitations to, a clinical investigations program. Fatal or life-threatening, unexpected ADRs occurring in *clinical investigations* qualify for very rapid reporting. Regulatory agencies should be notified (e.g., by telephone, facsimile transmission, or in writing) as soon as possible but no later than *7 calendar days after first knowledge by the sponsor that a case qualifies, followed by as complete a report as possible within 8 additional*

calendar days. This report must include an assessment of the importance and implication of the findings, including relevant previous experience with the same or similar medicinal products.

- **All Other Serious, Unexpected ADRs**

Serious, unexpected reactions (ADRs) that are not fatal or life-threatening must be filed as soon as possible but *no later than 15 calendar days* after first knowledge by the sponsor that the case meets the minimum criteria for expedited reporting.

- **Minimum criteria for reporting**

Information for final description and evaluation of a case report may not be available within the required time frames for reporting outlined above. Nevertheless, for regulatory purposes, initial reports should be submitted within the prescribed time as long as the following minimum criteria are met: an identifiable patient; a suspect medicinal product; an identifiable reporting source; and an event or outcome that can be identified as serious and unexpected, and for which, in clinical investigation cases, there is a reasonable suspected causal relationship. Follow-up information should be actively sought and submitted as it becomes available.

- **How to Report**

The CIOMS-I form has been a widely accepted standard for expedited adverse event reporting. However, no matter what the form or format used, it is important that certain basic information/data elements, when available, be included with any expedited report, whether in a tabular or narrative presentation. The listing in Attachment 1 addresses those data elements regarded as desirable; if all are not available at the time of expedited reporting, efforts should be made to obtain them.

All reports must be sent to those regulators or other official parties requiring them (as appropriate for the local situation) in countries where the drug is under development.

4.8. Safety Oversight - Data Safety Monitoring Board (DSMB)

A Data and Safety Monitoring Board (DSMB) will be formed by the Ethical Review Committee to evaluate and assess the safety of study participants. The DSMB will be composed of 3-5 members, three of which are nominated by the ERC chairperson. The PI also has the option of nominating 1 or 2 members with clinical expertise. The DSMB will convene two times, at the beginning before the trial is started, and at the end of the trial. Medical monitor will review the safety and have the option of convening a DSMB meeting if there is a safety issue that requires additional interpretation. The PI can also request a DSMB meeting depending upon the study complexity or in light of safety concerns. The DSMB will review all unanticipated problems involving risk to the participants or others, serious adverse events, and all participant deaths associated with the protocol. The DSMB will advise the PI of its findings and provide recommendations. The PI will inform the Sponsor in detail about the discussions of those meetings.

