4.6. Start of Trial and End of Trial

Trial starts once the participant has signed the informed consent form. The end of trial is defined as database lock after completion of the study by the last patient. A participant is considered to have completed the study if he or she has completed all phases of the study including the last visit or the last scheduled procedure shown in **Appendix I**.

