6.6. Interim Analyses

No interim analysis is currently planned.

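### No by-arm safety review is scheduled while patients are being dosed, so all 75 active-arm patients can be treated before the first planned comparison of harm between arms

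*Combined protocol and SAP*

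**What the plan says.** **Scheduled meetings.** Section 4.8: "The DSMB will convene two times, at the beginning before the trial is started, and at the end of the trial". Section 4.6 fixes the later date: "The end of trial is defined as database lock after completion of the study by the last patient".

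**What happens in between.** Section 4.8 gives the board a duty: "The DSMB will review all unanticipated problems involving risk to the participants or others, serious adverse events, and all participant deaths". Section 4.7.5 supplies the cases: "All SAEs should be reported to local DSMB within 24 hours of known information by the PI/investigators". Two routes to an extra meeting are open, both discretionary. One is through the monitor, "Medical monitor will review the safety and have the option of convening a DSMB meeting"; the other is through the investigator, "The PI can also request a DSMB meeting depending upon the study complexity or in light of safety concerns".

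**Comparison by arm.** Section 6.6: "No interim analysis is currently planned". Section 6.0 places the analysis at the end of the trial. Section 6.4 includes a comparison of AE and SAE percentages between arms and gives it no earlier date. Under section 4.4.6.1 the biostatisticians receive the randomization tables only after the study. Under section 4.4.6.2 the site is blinded and the sponsor keeps the list.

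**Stopping.** Section 4.11 deals with individual participants. No section visible in these documents names an event, or a number of events, that makes a board meeting compulsory.

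**The concern.** A monitoring board adds to case-by-case safety review mainly because it can set the arms side by side while patients can still benefit. On this schedule its fixed meetings fall before the first dose and after the last one.

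The setting makes single cases hard to read. Participants arrive with severe dehydration from cholera, so a serious event has a ready explanation other than study product, and those judging causality are blinded. A moderate excess in the active arm may be visible only as a difference in rates. Section 4.7.2 itself lists a clinically important rise in the rate of an expected serious reaction as grounds for rapid communication, yet no one is assigned to watch rates by arm. Non-serious events and laboratory changes, which could be the earlier signal, are not routed to the board at all.

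Section 4.0 describes the product as a novel fixed-dose combination, and the reassurance on risk in section 8.1 draws on data for the individual ingredients. What is at stake is participant protection. The primary efficacy analysis is not affected.

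**Working it through.** **1. Count from the text (no assumptions needed).**

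| Item | Source | Count |
|---|---|---|
| DSMB meetings scheduled during dosing | 4.8, with 4.6 | 0 |
| Events that oblige a meeting | 4.7.5, 4.8, 4.11 | 0 |
| By-arm safety comparisons planned before the end | 4.4.6.1, 6.0, 6.4, 6.6 | 0 |
| Active-arm patients who can be dosed before the first planned comparison | 4.0, 8.1 | 75 of 75 |

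If the end of the trial in 4.8 were read as the last patient's completion and not as database lock, the counts would be the same, because dosing would still be over.

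**2. Where the 75 comes from.** Section 5.0 assumes mean 280 and SD 156 g/kg, a 33% reduction and a two-sided t-test at 5%. The difference is 0.33 × 280 = 92.4. The noncentrality is (92.4/156) × √(n/2).

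- n = 75: 0.592 × 6.124 = 3.63, power 0.950 (plan: 0.94).
- n = 50: 0.592 × 5 = 2.96, power 0.835 (plan: 0.82).

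Both agree with the plan to within two points, so 75 per arm is the right exposure figure.

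**3. What the existing case flow would show.** The documents give no AE or SAE rates, so the active-arm SAE rates r below are assumptions. Expected cases are 75r. The chance of at least one case in the first 38 active patients is 1 − (1 − r)^38.

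| r | Expected among 75 | At least one in first 38 |
|---|---|---|
| 1% | 0.75 | 32% |
| 2% | 1.5 | 54% |
| 5% | 3.75 | 86% |
| 10% | 7.5 | 98% |

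Individual cases would therefore often reach the board early. What is missing is a required comparison between arms.

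**4. What one half-way by-arm review would add.** With 75 patients treated at 1:1, each arm has about 38, leaving 75 − 38 = 37 active-arm patients. This is an upper bound, because enrolment may continue while tables are prepared.

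Formal sensitivity is low. At 38 per arm, a split of 0 against 4 gives one-sided Fisher p = (38·37·36·35)/(76·75·74·73) = 0.058. A split of 0 against 5 gives that value × 34/72 = 0.027. So at least five events against none are needed for p ≤ 0.05. Summing the binomial probabilities of all splits with p ≤ 0.05:

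| Assumed rates, active vs placebo | Chance of p ≤ 0.05 at 38 per arm |
|---|---|
| 10% vs 1% | 0.25 |
| 5% vs 1% | 0.03 |
| 2% vs 1% | 0.001 |

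With a looser 0.10 level and more frequent harms, 20% vs 5% is flagged with probability 0.69 at 38 per arm and 0.92 at 75; 10% vs 2% gives 0.38 and 0.68.

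**The case against.** The best defence is that oversight between the two meetings is real. The medical monitor's safety review is an obligation; only the calling of a meeting is optional. The board must review SAEs, deaths and unanticipated problems, and it hears of SAEs within a day. Section 4.7.5 adds 7-day and 15-day regulatory reports, section 8.2 adds prompt reporting to the ethics committee, and section 7.0 speaks of periodic assessment of risk against benefit.

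All of that stands, and it rules out several stronger readings that a reader might infer:

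- *That the board cannot meet during dosing.* It can, at the monitor's or PI's initiative.
- *That nobody reviews safety during dosing.* Case-level review is required.
- *That unblinded data are out of reach.* The sponsor holds the list, and section 4.4.6.2 gives the board a part in emergency code breaks. An earlier comparison is possible but not required.
- *That no trigger exists anywhere.* A DSMB charter, if there is one, is not among these documents, and some text before section 4.4.3 is redacted.

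The safeguards still do not supply a look by arm. They work on one case at a time. Section 4.7.2 also treats expedited reporting as inappropriate for serious events considered unrelated, so an event wrongly attributed to cholera would bypass that route. Section 7.0 gives no dates, tables or actions.

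A second objection is that a half-way look would rarely reach significance. That is correct, and no claim of statistical detection is made for it.

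**Conclusion.** The point holds as a statement about what is scheduled and what is obligatory. No board meeting and no by-arm safety comparison is required between the first dose and the last, and all 75 active-arm patients can be dosed before the first planned comparison. That follows from the text and needs no assumed rate.

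The benefit of a mid-trial review is less certain. It rests on rates the documents do not give, and the formal sensitivity at 38 per arm is poor (0.25 even for 10% against 1%). What the review offers is informed judgement on SAEs, non-serious AEs and laboratory results together, before up to about 37 further active-arm exposures. Because it is cheap and affects no efficacy inference, it should be added.

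**What to change.** In section 4.8:

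1. Add one scheduled DSMB safety review when about 75 of the 150 patients have completed treatment. Supply AE, SAE and laboratory tables by arm, prepared from the existing randomization list by someone already independent of the blinded study team and sent to the board only. Limit it to safety data. With no efficacy test there is no alpha cost, and section 6.6 can say so.
2. State that the board will decide, at its already planned pre-start meeting, which events oblige an ad hoc meeting, and will record that decision.

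The protocol should not set a threshold or an enrolment-hold rule here. A simple count trigger illustrates the difficulty. If both arms had an assumed 1% rate of related SAEs, two or more among 150 patients would occur with probability 1 − 0.99^150 − 150 × 0.01 × 0.99^149 = 0.44. Such a count would also depend on blinded judgements of relatedness. The choice belongs with the board.

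Cost: protocol wording, one more meeting of the existing board and one set of safety tables. No extra patients or committee are needed. The main limitation is the low sensitivity shown above, so an unremarkable half-way review must not be reported as evidence of safety.

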4.9. Case management

From screening to discharge, patients' safety will be ensured through following procedures, which are also indicated in **Table 4: schedule of activities**. Screening procedures will be started only after obtaining written informed consent. During screening, medical and medication history will be collected and patients' condition will be monitored through physical examination, obtaining vital signs, assessment of stool and urine output vomiting, dehydration status, water intake, ORS intake and IV fluid infused, and testing for complete blood count (CBC) and serum electrolytes and creatinine. For female of child bearing age pregnancy will also be evaluated as a part of the exclusion criteria. All the inclusion and exclusion criteria will be strictly maintained for enrollment of the patients in the study, and no vulnerable participants will be enrolled. After randomization and administration

of IP/placebo, physical examination will be performed and vital signs will be obtained for initial three hours followed by at least 8 hourly for the whole treatment period and also at the end of treatment. Assessment of hydration status, including dehydration, vomiting, urine output, water intake, ORS intake or IV fluid infusion will be performed throughout the treatment period. Concomitant medication review will also be performed at least once in a day. Blood testing for the re-evaluation of the patient will be done according to the clinical condition of the patient and once at the end of treatment. Beside giving study specific treatment, all patients will be provided standard care and treatments. Standard of care (SoC) for adult cholera patients having severe dehydration includes rehydration with IV cholera saline (100ml/kg over 3 hours) and Doxycycline 300 mg after initial hydration; SoC also includes replacement of ongoing purging with ORS (if no persistent vomiting or no high purging) or IV fluid (if there is persistent vomiting or high purging). Adverse events, including SAE will be closely monitored, and appropriate treatment will be provided; if needed, patients will be referred to specialized clinics or hospitals. Recovery from diarrhoea will be assessed continuously through stool output and frequency, and stool culture will be performed to confirm the absence of *V. cholerae*. Feeding with a normal diet will be continued /initiated based on clinical feasibility; feeding with a normal diet will be resumed when vomiting has stopped and patients are able to tolerate oral intake. Patients will be fed meals prepared and dispensed under hygienic conditions. Street food will be prohibited due to the high risk of bacterial contamination, which may hinder case management and also invalidate the results of this study. Patients will receive 2 to 3 cooked meals per day. Even after discharge, health and wellbeing of the participants will be followed up with weekly phone calls or home visits; it will be ascertained if they are experiencing any side effects of the treatment or any other AE or SAE.

4.10. Concomitant Therapy

4.10.1. Prohibited Concomitant Therapy

Medications that have shown a positive effect on any aspect of diarrhea will not be permitted during the trial, including:

- Cholestyramine
- EGF/urogastrone
- Loperamide
- Racecadotril
- Somatostatin
- Alosetron
- Mytesi (Crofelemer)
- Atropine/dyphenoxilate

4.10.2. Permitted Concomitant Therapy

Concomitant therapy should be administered to all patients in accordance with the icddr,b guidelines on the treatment of cholera patients with acute diarrhea. Important steps are listed below (**Table 5**).

Table 5-Assessment of dehydration status ⁽¹⁰⁾

Assess	Condition*	Normal	Irritable/Less active*	Lethargic / Comatose*
	Eyes	Normal	Sunken	Sunken
	Tongue	Normal	Dry	Dry
	Thirst*	Normal	Thirsty (drinks eagerly)	Unable to drink*
	Skin pulse*	Normal	Goes back slowly*	Goes back very slowly*
	Radial pulse*	Normal	Reduced*	Uncountable or absent*

Diagnosis		No sign of dehydration	If at least 2 signs including one (*) sign is present, diagnose. Some Dehydration	If some dehydration plus one of the (*) signs are present, diagnose Severe Dehydration
Management		A	B	C

A. No sign of dehydration – ORS

- 50 ml ORS per kg body weight over 4-6 hrs *plus* ongoing losses
- Send patient to home with 4 packets of ORS
- Continue feeding, including breast milk for infants and young children on

B. Some dehydration – ORS

- 80 ml ORS per kg body weight over 4 – 6 hours *plus* ongoing losses
- Observe patients for 6 - 12 hours.
- Continue feeding, including breast milk for infants and young children on breastfeeding
- Reassess patients and dehydration status frequently - hourly.

In case of frequent vomiting (>3 times in 1 hour) or some dehydration persists ≥6 hours even after oral rehydration therapy: Treat with I/V fluid

C. Severe dehydration – I/V solution containing sodium, potassium, chloride and bicarbonate (e.g. Ringer's Lactate/ cholera saline)

Start I/V fluid immediately:

- 100 ml / kg Adult and Children > 1 year
30 ml / kg in first 1/2 hour
70 ml / kg in next 2.5 hours
- Encourage the patient to take ORS solution as soon as he/she is able to drink without vomiting.
- Antibiotic, if needed, after full rehydration.
- Zinc-20 mg/day for 10 days in children 6 months-5 yr old.

4.10.3. Antibiotic Therapy

Stool samples for *V. cholerae* dark field microscopy and culture should be collected before the onset of antibiotic therapy for presumed cases of cholera (Profuse watery stools, typically looking like 'rice water', resulting dehydration; many individuals affected in the same locality).

- Adults : Azithromycin, 1 gram single dose orally
- Repeat dose if vomiting within 1/2 hour of taking the medicine

Do not use azithromycin when a patient is 60-65 years or older or at any age with an established heart disease to avoid adverse effects, specially conduction defects.

In such a case, Doxycycline 300 mg single dose is recommended.

Antibiotics should be administered no sooner than 2 hours after taking VR-AD-1005.

4.11. Discontinuation of Trial Intervention and Participant Withdrawal from Trial

Participants may withdraw from a research study for any reason, even without mentioning any reason. The participants will be able to receive standard treatment of the hospital without any penalty. For evaluation and reporting purposes, researchers may ask participants for their reasons for early withdrawal.

An investigator may discontinue trial intervention or withdraw a participant from the study for the following reasons:

- Significant study intervention non-compliance.
- If any adverse event (AE), Serious adverse events (SAE), laboratory abnormality, or other medical condition or situation occurs, continued participation in the study would not be in the best interest of the participant.
- Disease progression which requires discontinuation of the study intervention
- If the participant meets an exclusion criterion (either newly developed or not previously recognized) that precludes further study participation.
- Participant unable to receive study intervention for 3 days.
- Reporting over-dose
- protect a participant from excessive risk or risk with a demonstrated lack of benefits (e.g., a participant experiences serious side-effect without the anticipated therapeutic effects), or
- maintain the integrity of the data (e.g., a participant is not following study procedures or may be deliberately providing false information).

Whenever an investigator terminates a subject's participation in research, the investigator must explain to the participant the reasons for the termination and, as appropriate, other treatment options available to the participant.

The data to be collected at the time of study intervention discontinuation will include the following:

- Physical examination
- Vital signs
- Complete blood count (CBC)
- Blood Basic metabolic panel, including Serum electrolytes and creatinine
- Assessment of vomiting
- Assessment of stool output
- Assessment of dehydration
- Assessment of IV and oral ORS and oral water intake
- Assessment of urine output
- Administration of questionnaires or other instruments helping participants to register symptoms, such as stool charts.
- Assessment of adverse events.

Follow-up calls will be made with patients who completed the protocol with questionnaires focusing on the side effects. Calls will be made once a week during the 28-day follow-up period.

If any serious adverse events occur before treatment phase, study treatment may be postponed at the researcher's decision.

The reason for participant discontinuation or withdrawal from the study will be recorded on the CRF. Subjects who sign the informed consent form and are randomized but do not receive the study intervention may be replaced. Subjects who sign the informed consent form, and are randomized and receive the study intervention, and subsequently withdraw, or are withdrawn or discontinued from the study, will not be replaced.

4.12. Lost to Follow-up

A participant will be considered lost to follow-up if he or she fails to return for three out of four scheduled phone calls or one missed in-person visit (for withdrawals) and is unable to be contacted by the study site staff. The following actions must be taken if a participant fails to return to the clinic for a required study visit: The site will attempt to contact the participant and reschedule the missed visit within 7 days and counsel the participant on the importance of maintaining the assigned visit schedule and ascertain if the participant wishes to and/or should continue in the study.

Before a participant is deemed lost to follow-up, the investigator or designee will make every effort to regain contact with the participant (where possible, 3 telephone calls and/or electronic messages, one home visit). These contact attempts should be documented in the participant's medical record or study file.

Should the participant continue to be unreachable, he or she will be considered to have been lost to follow-up and will be excluded from the long-term safety data analysis.

Since follow-up occurs after the completion of the treatment course, loss to follow-up is not critical for the primary and secondary endpoints and treatment data obtained during the course of the trial will remain valid.

